10.6.2 Secondary Outcomes

Symptom severity scores will be determined from the COVID-19 symptom PROs reported daily by participants. Each symptom is rated by the participant on a scale from 0-4. Although the seriousness of the symptoms are not equal, summing the individual symptom ratings will give a rough measure of the participant's disease severity. These daily symptom severity scores will be summed over the 28-day period using area under the curve (AUC). Comparisons of this AUC, as well as weekly symptom severity scores, by age, race/ethnicity, gender, risk group and assigned treatment will be performed using Wilcoxon rank sum tests. For this, and all comparisons by demographic or treatment variables, the results will be considered for planning purposes only. Secondary outcomes 2, 3, and 4 involve compliance proportions and will be documented in total and compared by demographic and treatment variables using Fisher exact tests. Secondary outcomes 5, 6, and 7 involve event rates which will be calculated in total and compared by demographic and treatment variables using negative binomial regression. Detectable versus not detectable SARS-CoV-2 RNA from nasal swabs at days 7 and 14 will be compared by demographic and treatment variables using Fisher exact tests, and continuous measures of SARS-CoV-2 RNA (on log10 scale) will be assessed for normality and tested using t-tests or Wilcoxon rank sum tests, as appropriate.

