6.2.9 Study Day 1 (day of first study substance administration) – Remote

Study staff will confirm the first dose taken by the participant by telephone. Participants who refuse the first dose after 2 days will be discontinued from the study.

Study staff will also confirm by telephone the completion of first nasal swab home kit to be mailed out within 24 hours. The nasal swab home kit can be completed within days 1 to 3 to accommodate shipping limitations.

The participant will utilize an application (app) available to self-report symptoms once daily as Patient-reported outcomes (PRO). The application clarifies to the study participant the information they are providing is not a substitute for standard COVID-19 care with their health care provider. The participant's completion of the self-report or PRO will be reviewed. If the participant does not complete their self-report, study staff will initiate contact to facilitate the completion of the daily self-report PRO. If the self-report or PRO discloses onset or worsening of the symptom of shortness of breath or worsening of other symptoms the participant will be instructed to call 911, telephone their health care provider or go to the health care provider urgent or emergency care facility.

Study staff will obtain and review the participant's EHR for pertinent information for the primary, secondary and exploratory endpoints.

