6.2.18 COVID-19 Symptom Screen

Participants will be asked about their first symptoms related to COVID-19 and their current symptoms, to document eligibility. This will include when and what symptoms the participant noticed having. This data will be collected via the Study App.

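### The arm comparison of the 28-day symptom AUC and weekly scores makes no use of starting symptom level, so it gives up some precision; the planned test remains valid

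*Combined protocol and SAP*

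**What the plan says.** Section 10.6.2 builds the outcome in three steps. First, "Each symptom is rated by the participant on a scale from 0-4". The ratings are then added across symptoms to give a daily score. Finally, "These daily symptom severity scores will be summed over the 28-day period using area under the curve (AUC"). For the comparison it says that "Comparisons of this AUC, as well as weekly symptom severity scores, by age, race/ethnicity, gender, risk group and assigned treatment will be performed using Wilcoxon" (the rank sum test). Age, race/ethnicity, gender and risk group appear there as separate grouping variables, not as adjustments to the treatment contrast. No section uses a starting symptom level, a change from baseline or a stratified test for this outcome. Section 10.6.1 does allow covariate adjustment, but only for the primary health events. Randomisation is stratified by age and comorbidity risk (3.3, 10.3), not by symptom burden.

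Symptom information exists before treatment. Section 6.2.18 says: "Participants will be asked about their first symptoms related to COVID-19 and their current symptoms, to document eligibility". It adds: "This will include when and what symptoms the participant noticed having". The schedule in 6.1 places this screen at the screening visit, and under 6.2.6 randomisation follows confirmed eligibility. Daily reporting is described from Day 1: "The participant will utilize an application (app) available to self-report symptoms once daily as Patient-reported outcomes (PRO").

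**The concern.** An AUC of summed symptom scores tends to carry the participant's starting state into the outcome: someone who enters with many symptoms is likely to accumulate a larger total in either arm. Entry under 4.2.4 runs from a single mild symptom to moderate illness with breathlessness on exertion, so starting burden can be expected to differ between participants, and the design does not balance it. Variation that a baseline measure could explain stays in the error term of the rank sum test.

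The stake is efficiency. Section 10.2 intends these outcome measures for the analysis plan of future studies. The pilot's clinical endpoint is sparse: at the 0.20 and 0.10 rates in 10.4, 30 × 0.20 + 30 × 0.10 = 9 hospitalisations or deaths are expected. The symptom score is therefore one of the few measures from which a 60-person pilot can learn much about efficacy, and a sharper estimate of it would help planning.

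**Working it through.** The plan states no SD, effect size, power or precision for the symptom AUC, so there is no figure of its own to reproduce. The relative-risk interval in 10.4 concerns hospitalisation or death and is not an input here.

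**Inputs.** From the documents: 30 per arm (Section 3), 1:1 allocation (10.3), Wilcoxon rank sum test (10.6.2). Assumed, because the documents are silent: two-sided 5%, a treatment effect of 0.5 SD, and a correlation ρ of 0.3, 0.5 or 0.7 between underlying baseline severity and the AUC.

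**Chance imbalance.** The difference between arm means at baseline has SD √(2/30) = 0.258 baseline SDs, and the probability that it exceeds 0.25 SD in either direction is 33%. An imbalance reaches the AUC multiplied by ρ, so one of 0.258 SD moves the AUC contrast by 0.08, 0.13 or 0.18 AUC SDs at ρ = 0.3, 0.5 or 0.7.

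**Variance.** A linear adjustment multiplies the variance of the arm contrast by 1 − ρ², which gives 0.91, 0.75 and 0.51. The standard error is multiplied by 0.95, 0.87 and 0.71.

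**Formula power for a scored baseline.** Power ≈ Φ(0.5 / (0.258·√(1 − ρ²)) − 1.96). Unadjusted this is Φ(1.936 − 1.96) = 0.49. Adjusted it is 0.53, 0.61 and 0.77.

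**Simulation of the actual tests.** The Wilcoxon test was compared with ANCOVA on ranks at 30 per arm, with 4,000 trials per setting for a fully scored baseline. The Monte Carlo standard error of a single power figure is then at most √(0.25/4000) = 0.008. Two baselines were used. One is a continuous score. The other is a count of 10 yes/no symptoms, closer to what 6.2.18 describes, with assumed loading 0.6 and prevalence 35%. Wilcoxon power is about 0.45 throughout.

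| Assumed ρ | Gain, screening count (points) | Gain, scored baseline (points) |
|---|---|---|
| 0.3 | about 3 | about 3 |
| 0.5 | about 8 | about 11 |
| 0.7 | about 16 | about 24 |

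For the scored baseline, repeat runs gave 3 to 4, 10 to 12 and 24 to 26 points. Counts of 6 or 12 items gave about 2, 6 to 8 and 14 to 18. At ρ = 0 the two tests have power 0.454 and 0.459, so the extra term costs nothing visible. Type I error is about 0.05 for both tests. These figures are for the AUC; the weekly scores were not simulated separately.

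**The case against.** The strongest reply is that nothing is wrong with the planned test. Under randomisation the Wilcoxon test already allows for chance imbalance, and simulated type I error is about 0.05 with or without adjustment. A reader might infer that a chance baseline imbalance could pass for a treatment effect. The documents do not support that as a fault of the plan: the false-positive rate is controlled, and an imbalance carries through only in proportion to ρ.

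The size is also uncertain. The documents give no ρ. Screening falls early in a changing illness, since treatment must start within 96 hours of symptom onset (6.2.7), while the outcome covers 28 days, so a low correlation is plausible and the gain may be only about 3 points. A reader might also take the scored-baseline figure at ρ = 0.5 as the expected benefit, equivalent to 60 / 0.75 = 80 participants. Section 6.2.18 does not support that: it describes which symptoms were noticed and when, not 0-4 ratings, and a count recovers less.

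Power is a limited yardstick here. Section 10.6 says the pilot is not powered for arm differences, 10.6.2 labels these comparisons as planning only, and 10.4 warns against taking effect sizes from pilots. Nor is the symptom score the only efficacy measure besides hospitalisation: log10 viral RNA is also compared, in a subset.

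All of this stands, and it limits the point to an efficiency improvement. It does not remove it, because the covariate is already collected and adjustment costs almost nothing even when ρ is zero. The planning-only label favours an adjusted estimate with an interval over a bare rank test.

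**Conclusion.** The point holds as a minor, low-cost gain in precision. Section 10.6.2 leaves out starting symptom burden although 6.2.18 collects current symptoms before randomisation. The gain ranges from slight at the low end of the assumed correlations to useful at the high end, and the documents cannot say where in that range the trial lies. The count-based figures rest further on the assumed checklist length, loading and prevalence. There is no bias, no inflated error rate and no threat to the trial's conclusions.

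**What to change.** In 10.6.2, for the treatment comparison of the AUC and the weekly scores:

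- Use a rank ANCOVA: regress the ranked outcome on arm and the ranked number of current symptoms from the 6.2.18 screen. State the symptom list from which the count is taken.
- Keep the unadjusted Wilcoxon test as a sensitivity analysis.
- Also report a baseline-adjusted difference with its interval on the symptom-score or log-score scale. A difference in mean ranks alone has no units that a later sample-size calculation can use.
- Use the Day 1 score as the covariate only if it is confirmed as entered before the first dose, and in that case leave it out of the AUC. Section 6.2.9 defines "Study Day 1 (day of first study substance administration") without requiring the report to come first, so a Day 1 score could otherwise be post-treatment and could count in both covariate and outcome.

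With the screening count, no new visit or data item is needed. The cost is one degree of freedom and a few lines of analysis, and the comparison keeps its secondary, planning-only status. A fully scored baseline would additionally need a specified 0-4 report before the first dose.

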3.3 Stratification

Randomization will be stratified by “high” versus “low” risk of severe disease, where “high” risk is defined by any of the following:

- Patients aged 60 years and older
- Patients having at least one of the following conditions under control:
 - Chronic lung disease including pulmonary fibrosis, COPD, pulmonary hypertension, moderate to severe asthma
 - Immunocompromised status due to disease (for example, those living with HIV with a CD4+ T-cell count of <200/mm³)
 - Immunocompromised status due to medication (for example, persons taking 5 mg or more of prednisone equivalents a day, cancer therapies)
 - Solid organ transplant, hematologic stem cell transplant, rheumatological disease or inflammatory bowel disease on immunosuppressants
 - Severe obesity (body mass index [BMI] >40; may be based on self-report of height and weight)
 - Hypertension requiring treatment by more than one agent.
 - Cardiovascular disease including coronary artery disease, congestive heart failure, valvular heart disease
 - Diabetes
 - Chronic kidney disease including stage 3-4 CKD.
 - Chronic liver disease including cirrhosis, autoimmune hepatitis, uncontrolled hepatitis.

4. SELECTION AND ENROLLMENT OF PARTICIPANTS**4.1 Recruitment****4.1.1 Recruitment**

This trial will recruit study participants through community health care sites and programs (Appendix 2 that lists the initial site) that are performing SARS-CoV-2 testing of symptomatic patients. The initial site is based in Los Angeles County.

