4.3.7 Known allergy/sensitivity or any hypersensitivity to components of XFBD

4.3.8 Active drug or alcohol use or dependence that, in the opinion of the site investigator, would interfere with adherence to study requirements.

4.3.9 Has known prior kidney disease.

4.3.10 Has known cirrhosis, acute liver disease or uncontrolled chronic liver disease.

4.3.11 Has known severe coronary artery disease.

4.3.12 Has known narrow angle glaucoma.

4.3.13 Has greater than two or a single uncontrolled underlying comorbid condition including cardiovascular disease (coronary artery disease, heart failure, valvular heart disease), hypertension, diabetes, chronic lung disease, chronic kidney disease, chronic liver disease, immunocompromised (HIV or daily users of more than 5 mg/day of prednisone), prior organ transplant.

4.3.14 Fulfils the FDA EUA criteria of at high risk for progressing to severe COVID-19. This includes high-risk individuals specified in the EUA who meet at least one of the following criteria: Body mass index (BMI) \geq 35; Chronic kidney disease; Diabetes mellitus; Immunocompromising condition/immunosuppressive disease; Currently receiving immunosuppressive treatment; Aged \geq 65 years; or Aged \geq 55 years and have: Cardiovascular disease, or Hypertension, or Chronic obstructive pulmonary disease/other chronic respiratory disease. If the patient is not able to receive the EUA agent because of unavailability this exclusion may be waived.

4.3.15 Women who are currently pregnant or breastfeeding.

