10.2.2 Secondary Outcome Measures

- 10.2.2.1 To document the effect of XFBD on Symptom Severity Score within 28 days of

study entry.

- 10.2.2.2 To document the proportion of patients who are compliant taking greater than 90% of the test substance as measured by self-report
- 10.2.2.3 To document the proportion of patients who comply with symptom monitoring.
- 10.2.2.4 To document the proportion of patients who comply with repeated clinical testing.
- 10.2.2.5 To document cumulative incidence of serious adverse events, and adverse events leading to early discontinuation of XFBD or placebo.
- 10.2.2.6 To document cumulative incidence of grade 3 and 4 adverse events.
- 10.2.2.7 To obtain levels (detectable versus not detectable, and continuous on log10 scale) of SARS-CoV-2 RNA from nasal swabs at approximately days 1, 7 and 14 among a subset.

10.3 *Randomization and Stratification*

[figure not shown]
Eligible participants will be randomized using a 1:1 ratio to each of the study arms. Housemates of participants previously enrolled will be independently randomized so that housemates will not be clustered within treatment group.

Randomization will be stratified by “high” vs “low” risk of severe disease, where “high” risk is defined by any of the following: age ≥ 60 years, or having any of a number of conditions, as described in section 3.3.

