10.6 Analyses

All descriptive statistics will be documented in total and stratified by age, race/ethnicity, gender, risk group and assigned treatment, when applicable. This pilot study is not powered to find statistically significant differences by treatment group.

All analyses involving randomized comparisons will include all randomized participants who received the first (**confirmed**) dose of study treatment, according to a modified intention-to-treat approach. However, as the study is blinded, the use of a modified intention-to-treat approach should not introduce bias into the comparison of randomized arms in this pilot study or in future larger-scale studies.

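### The between-arm comparison of the 28-day symptom AUC and weekly scores uses an unstratified Wilcoxon test although randomisation is stratified by risk group

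*Combined protocol and SAP*

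**What the plan says.** Section 10.6.2 adds up the participant's daily 0-4 symptom ratings and accumulates the totals over 28 days as an AUC. Comparisons of this AUC and of the weekly scores "by age, race/ethnicity, gender, risk group and assigned treatment will be performed using Wilcoxon rank sum tests". For these comparisons, "the results will be considered for planning purposes only".

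The randomisation has a stratum. Section 3.3: "Randomization will be stratified by “high” versus “low” risk of severe disease". Section 10.3 repeats it: "Randomization will be stratified by “high” vs “low” risk of severe disease". Section 10.6.1 allows stratified or covariate-adjusted regression, but only for the two primary outcomes that are health events. The stratification mentioned in section 10.6 concerns descriptive statistics.

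Two other provisions bear on the size of the point. Exclusion 4.3.14 removes anyone who "Fulfils the FDA EUA criteria of at high risk for progressing to severe COVID-19", with the proviso "If the patient is not able to receive the EUA agent because of unavailability this exclusion may be waived". Section 10.6 sets the analysis population: "All analyses involving randomized comparisons will include all randomized participants who received the first" confirmed dose.

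**The concern.** When allocation is stratified on a factor that also predicts the outcome, the arms are balanced on it by design. An analysis that ignores the factor leaves the between-stratum spread in the reference variance, even though the balanced design has taken that spread out of the treatment contrast. The test then rejects too rarely when there is no effect and has less power when there is one. High-risk participants may well report more or longer symptoms, so the condition is plausible here, but the documents give no data on it.

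The stake is efficiency in an already small comparison. Section 10.2 also says that these outcome measures will be used in the analysis plan of the future studies. It carries over the measures rather than the pilot's tests, but a sound template is easy to set now.

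**Working it through.** **Inputs from the documents.** 60 participants, 30 per arm, 1:1 (sections 3 and 10.3); two risk strata (3.3, 10.3); plain Wilcoxon test (10.6.2). The plan gives no alpha, effect size, SD or power for the AUC, so it has no figure of its own to reproduce.

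**Assumptions.** Two-sided 5% level; normal scores with SD 1 within strata; 0.75 SD treatment effect; high-risk stratum shifted by g = 0.5 or 1.0 SD; high-risk share p from 10% to 50%, equal in both arms.

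**Step 1: why the plain test is conservative.** Ignoring the strata raises the variance that the test uses from 1 to 1 + p(1 − p)g², while the balanced contrast still varies as if that variance were 1. In the normal approximation, the effective critical value is 1.96 × √(1 + p(1 − p)g²).
- p = 10%, g = 0.5: 1 + 0.0225 = 1.0225; critical value 1.982; rejection under the null 4.75%.
- p = 20%, g = 1.0: 1 + 0.16 = 1.16; critical value 2.111; 3.5%.
- p = 50%, g = 1.0: 1 + 0.25 = 1.25; critical value 2.191; 2.8%.

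Simulation of the rank tests agrees: 2.8-4.8% for the plain Wilcoxon test and 4.8-5.1% for van Elteren.

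**Step 2: power (simulation, 40,000 runs per setting, 0.75 SD effect).**

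| High-risk share | Stratum gap (SD) | Plain Wilcoxon | van Elteren | Gain (points) |
|---|---|---|---|---|
| 10% | 0.5 | 0.785 | 0.784 | −0.1 |
| 10% | 1.0 | 0.770 | 0.787 | 1.7 |
| 20% | 0.5 | 0.785 | 0.790 | 0.5 |
| 20% | 1.0 | 0.744 | 0.786 | 4.2 |
| 30% | 0.5 | 0.771 | 0.781 | 1.0 |
| 30% | 1.0 | 0.728 | 0.786 | 5.8 |
| 50% | 0.5 | 0.774 | 0.789 | 1.5 |
| 50% | 1.0 | 0.716 | 0.792 | 7.6 |

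A separate run of 10,000 gave gains of 4.6 points (20%, 1.0 SD: 0.746 v 0.792) and 7.9 points (50%, 1.0 SD: 0.713 v 0.792). Allowing for simulation error, the gain is about 0 to 5 points at 10-20% high risk and about 1 to 8 points at 30-50%.

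**Step 3: the price if risk group is irrelevant.** With no stratum gap, power is 0.792-0.796 for the plain test and 0.785-0.792 for van Elteren. The loss is 0.4-0.7 points, or 0.7-0.9 in the separate run, so under 1 point in both.

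**Step 4: which share is likely.** Section 3.3 counts diabetes, chronic kidney disease, immunocompromise and age 60 or over as high risk. Exclusion 4.3.14 removes diabetes, chronic kidney disease, immunosuppression, BMI 35 or more, age 65 or over, and age 55 or over with cardiovascular disease, hypertension or chronic respiratory disease. Exclusions 4.3.9 and 4.3.10 remove known kidney disease and cirrhosis. Unless the 4.3.14 waiver is used often, the high-risk stratum should be small, which points to the 10-20% rows.

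**Side note: days without a score.** At the section 10.4 rates, 0.20 × 30 = 6 placebo and 0.10 × 30 = 3 XFBD participants would be hospitalised or die by Day 42. This is an upper bound for Day 28. All of them who took a confirmed first dose are in the comparison. No readable section says how days in hospital, after death or without a report enter the AUC. Ranking all such participants worst would itself move the result. With no symptom effect, P(XFBD better) = 0.9 × 0.2 + 0.9 × 0.8 × 0.5 + 0.5 × 0.1 × 0.2 = 0.18 + 0.36 + 0.01 = 0.55.

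**The case against.** **Reviewer preference.** The plain test is valid and errs on the safe side. The pilot is declared unpowered, the comparison is for planning, and every power figure rests on an assumed effect and stratum gap. In one setting with a stratum gap (10% high risk, 0.5 SD) there is no gain at all. All of this stands, and it limits the importance. It is no reason to keep the plain test: the change is one sentence, its cost is under 1 point, and the plan already allows stratified models in section 10.6.1.

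**Stronger readings that a reader might infer.**
- *The unstratified test biases the comparison or inflates false positives.* It does neither; the null rejection rate falls below 5%.
- *Participants admitted early will rank as mild, so a benefit could be masked or reversed.* This requires unreported days to count as 0, which the plan nowhere says. Staff chase missed reports (6.2.9 to 6.2.14), daily questions can be answered by app or phone (6.1), and the app offers a no-symptoms answer (Appendix VI), so a blank need not mean zero. The silence is missing detail, not an error in itself.
- *Death and hospitalisation should rank worst in the main analysis.* That would turn the symptom objective (1.3.1) into a composite overlapping primary objective 1.2.4, and would give 0.55 in favour of XFBD with no symptom effect. It is suitable only as a sensitivity analysis.

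**Conclusion.** The point holds as a low-cost improvement. The treatment comparison of the AUC and weekly scores should respect the randomisation stratum, and as written it does not. That the test is unstratified is inferred from its name and from the absence of any stratum in section 10.6.2; no other readable section supplies one.

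Confidence in the textual point is high. The magnitudes depend on the assumed effect, stratum gap and high-risk share, none of which the documents give. The undefined handling of unreported days is worth settling alongside, but the documents do not support a claim that it distorts the result.

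**What to change.** 1. Add to section 10.6.2: *The 28-day AUC and weekly scores will be compared between treatment arms with a van Elteren test stratified by the randomised high/low risk group.* The Wilcoxon tests by demographic variables can stay.
2. Before unblinding, state one missing-day rule for the AUC that covers days in hospital, after death, after withdrawal and without a report. It should not score an unreported day as 0 unless the participant is confirmed symptom-free. One option is to interpolate between reports and carry the last score forward after the final one.
3. Add a sensitivity analysis in which death, then COVID-19 hospitalisation, by Day 28 rank worst. Keep the symptom AUC as the main analysis.

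The cost is wording only. Death and hospitalisation are already collected through record review, telephone contact and secondary contacts. The stratified test gives up under 1 power point if risk group is unrelated to symptoms, and the sensitivity analysis will partly repeat the hospitalisation outcome.

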1. HYPOTHESIS AND STUDY OBJECTIVES

1.1. *Hypothesis*

- 1.1.1. Xuanfei Baidiu granules (XFBD) will prevent hospitalization and death in persons with symptomatic SARS-CoV-2 infection.

1.2. *Primary Objective*

- 1.2.1. To document the feasibility of recruitment through community setting by assessment of the number of positive cases identified per week.
- 1.2.2. To document the proportion of patients who agree to participate as measured by enrollment and randomization.
- 1.2.3. To document the treatment emergent side effects and safety profile of the XFBD and placebo.
- 1.2.4. To document the rate of hospitalization or death within 42 days of enrollment in the XFBD and placebo treated groups.

1.3. *Secondary Objectives*

- 1.3.1. To document the effect of XFBD on Symptom Severity Score within 28 days of enrollment in the XFBD and placebo treatment.
- 1.3.2. To document the proportion of patients who are compliant taking greater than 90% of the test substance as measured by self-report
- 1.3.3. To document the proportion of patients who comply with symptom monitoring.
- 1.3.4. To document the proportion of patients who comply with repeated clinical testing.
- 1.3.5. To document the hospital-free days from enrollment to 42 days (number of days patient not in hospital).
- 1.3.6. To document cumulative incidence of serious adverse events, and adverse events leading to early discontinuation of XFBD or placebo.
- 1.3.7. To document cumulative incidence of grade 3 and 4 adverse events.
- 1.3.8. To obtain levels (detectable versus not detectable, and continuous on log10 scale) of SARS-CoV-2 RNA from nasal swabs at approximately days 1, 7 and 14 among a subset.

1.4. *Exploratory Objectives*

- 1.4.1. To document the rate of subjects tested as negative for SARS-CoV-2 at day 14.
- 1.4.2. To document the rate of housemate infection.
- 1.4.3. To document if XFBD changed the severity and duration of self-reported symptom experience of COVID-19.

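### Section 10.6.2 compares safety outcomes defined as cumulative incidence by negative binomial regression on undefined event rates, and its outcome numbers do not match the list in 10.2.2

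*Combined protocol and SAP*

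**What the plan says.** Section 10.2.2 (Secondary Outcome Measures) lists seven items. Item 5 reads "To document cumulative incidence of serious adverse events, and adverse events leading to early discontinuation of XFBD or placebo". Item 6 reads "To document cumulative incidence of grade 3 and 4 adverse events". Item 7 begins "To obtain levels (detectable versus not detectable, and continuous on log10 scale) of SARS-CoV-2 RNA from nasal swabs".

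Section 10.6.2 assigns the methods by number. Outcomes 2, 3 and 4 are compliance proportions, compared by Fisher's exact test. Outcomes 5, 6 and 7 all "involve event rates which will be calculated in total and compared by demographic and treatment variables using negative binomial regression". The sentence after that gives viral RNA separate methods without a number. It begins "Detectable versus not detectable SARS-CoV-2 RNA from nasal swabs at days 7 and 14 will be compared by demographic and treatment variables using Fisher exact"; of the log10 level it adds that this "will be assessed for normality and tested using t-tests or Wilcoxon rank sum tests, as appropriate".

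The objectives in section 1.3 form a longer list. Its item 5 is "To document the hospital-free days from enrollment to 42 days (number of days patient not in hospital"; the safety objectives follow as items 6 and 7, and RNA is item 8. Hospital-free days does not appear in 10.2.2.

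Three further statements bear on the point. Section 10.6.1 allows either logistic or negative binomial models for the primary health events, but 10.6.2 does not repeat the logistic option. Section 10.6 says that the pilot is not powered for treatment differences, and 10.6.2 says that its comparisons serve planning only. Section 10.2 says that these outcome measures will be carried into the SAP of future studies.

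**The concern.** Cumulative incidence over a fixed follow-up is a per-person quantity: did the participant have the event or not. Negative binomial regression models the number of events per person. The two answer different questions, and under the second a single participant with several events can drive the treatment ratio. The plan calls the outcomes event rates but defines neither the count nor the exposure time, so a programmer cannot tell which quantity is meant.

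Safety is one of this pilot's main purposes, and its outcome measures are meant to be reused. An analysis that may return no standard error, or no estimate at all when an arm is free of events, is a poor template for the later trial. The outcome numbers add a second ambiguity, because read against 10.2.2 the same sentence also covers viral RNA.

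**Working it through.** The plan states no figure that depends on this choice, so there is nothing of its own to reproduce. The check has four steps.

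**1. What the numbers point to.**

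| Number in 10.6.2 | List in 10.2.2 | List in 1.3 |
|---|---|---|
| 5 | SAEs; AE discontinuations | Hospital-free days |
| 6 | Grade 3-4 AEs | SAEs; AE discontinuations |
| 7 | Viral RNA | Grade 3-4 AEs |
| (8) | none | Viral RNA |

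Items 2 to 4 are the same in both lists, so they do not settle which list is meant. Read against 10.2.2, RNA has two incompatible methods in consecutive sentences. Read against 1.3, RNA has only its own tests, and negative binomial regression falls on hospital-free days. That is a day count bounded by the 42-day window, not an event rate. At the 20% and 10% event rates that 10.4 assumes for hospitalization or death, about 24 and 27 of 30 participants (30 - 6 and 30 - 3) would have no such event and so sit at the upper limit.

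**2. Model against outcome.** A yes/no outcome with probability p has variance p(1 - p), which is below its mean p. The negative binomial variance is m + a·m², with a ≥ 0, so it is never below the mean m. The fitted dispersion a is therefore pushed to its boundary at zero, where the model becomes Poisson. This always applies to AE discontinuation: section 9.1 treats discontinuation as permanent, so it happens at most once per person. It applies to SAEs and grade 3-4 AEs when they are summarised as participants with at least one event.

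**3. Standard error of the log ratio, n = 30 per arm (section 3), a and c participants with an event.**

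- Poisson limit: √(1/a + 1/c).
- Binomial: √(1/a - 1/n + 1/c - 1/n).
- With the same rate p in both arms, a = c = 30p and the ratio of the two reduces to 1/√(1 - p).

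| Assumed common rate | SE ratio |
|---|---|
| 2% | 1.010 |
| 5% | 1.026 |
| 10% | 1.054 |
| 20% | 1.118 |

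As an illustration, take the 10.4 rates, which give 6/30 against 3/30. The Poisson-limit SE is √(1/3 + 1/6) = 0.707. The binomial SE is √(0.5 - 2/30) = 0.658. The ratio is 1.074, so the SE is 7% too wide. A negative binomial fit to these 0/1 data in statsmodels gave a rate ratio of 0.50 and a dispersion of 0.0008, but its Hessian could not be inverted and no standard error was returned. Other software may return the Poisson-limit value. Fisher's exact test gives p = 0.47.

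The error is conservative. At a common rate of 20%, the exact type I error of a nominal 5% Wald test is 0.014 with the Poisson-limit SE and 0.027 with the binomial SE, counting tables with an empty arm as non-rejections.

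**4. Arms with no events.** P(no events in a given arm) = (1 - p)^30, and P(at least one arm empty) = 1 - [1 - (1 - p)^30]².

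| Assumed common rate | Given arm empty | At least one arm empty |
|---|---|---|
| 2% | 0.545 | 79% |
| 5% | 0.215 | 38% |
| 10% | 0.042 | 8% |

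In those cases the maximum likelihood log ratio does not exist. Logistic regression has the same weakness; Fisher's test and exact or Newcombe intervals do not. Section 10.6.2 also applies the method across demographic groups, some of which will be smaller than 30.

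**The case against.** The strongest reply is that SAEs and grade 3-4 AEs can recur under the definitions in section 7, and negative binomial regression is a legitimate model for events per participant. That stands. It would rescue the method for those two outcomes if the number of events were the stated target, but the outcome list says cumulative incidence, and no count or offset is given. It cannot rescue AE discontinuation. A reader might infer that every outcome in the sentence happens at most once; the documents support that only for discontinuation, or for the others once reduced to participants affected. Reading cumulative incidence as the proportion with at least one event is the usual meaning, but the protocol does not spell it out.

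A reader might also infer that the plan models viral load as a count. The RNA sentence and the order of the 1.3 list make a cross-reference slip the better explanation.

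Nor does it follow that the safety outcomes go unreported as stated. Section 10.6 provides descriptive statistics in total and by arm, and the model is only the comparison step. Finally, the comparisons are unpowered and for planning only, and no sample size or decision rule rests on them. That stands and limits the severity.

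**Conclusion.** The point holds, at low to moderate severity. The only comparison method named for the safety outcomes does not match cumulative incidence, and event rates are left undefined. For a 0/1 outcome the SE is too wide by about 1% to 12% at rates from 2% to 20%, in the conservative direction. The larger practical problem is an empty arm, at 79%, 38% and 8% for rates of 2%, 5% and 10%. All these rates are assumptions, because the documents give no AE rates.

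Figures of 15% or 21% for the SE can be reached by taking 9 against 6, or 12 against 8, of 30. Those counts need 20% to 40% of participants in an arm to have the event. Nothing in the documents supports that for SAEs, and section 7.1 excludes worsening COVID-19, including hospitalization or death due to it, from AEs and SAEs.

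The numbering mismatch needs no assumption. The sentence cannot be followed as written under either list: one gives RNA two methods, the other treats a bounded day count as an event rate.

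**What to change.** - Align 1.3, 10.2.2 and 10.6.2, restore hospital-free days to 10.2.2, and name outcomes in 10.6.2 instead of numbering them. Simply striking the 7 is not safe: under the 1.3 numbering it would remove the method for grade 3-4 AEs.
- Leave RNA with its Fisher and t-test or Wilcoxon methods only.
- Compare hospital-free days by Wilcoxon rank sum test, with allowance for the many ties expected at the upper limit.
- For SAEs, AE discontinuations and grade 3-4 AEs, report participants with at least one event (n/N) by arm and the risk difference with a Newcombe or exact interval. Use Fisher's exact test if a test is wanted, as 10.6.2 already does for the compliance proportions.
- List total event counts descriptively, or keep negative binomial regression only for recurrent event counts, with an offset for follow-up time.

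The cost is wording only; no data collection or sample size changes. The downside is that repeat events in one person no longer drive the main comparison, so the table of total counts has to show them.
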